## 4.2 Secondary Endpoints

- 1. Incidence of serious adverse events, defined as the proportion of participants with treatment-emergent serious adverse events and the number of treatment-emergent serious adverse events, overall, by system organ classification, by relatedness to study medication, and by severity
- 2. Incidence of non-serious adverse events, defined as the proportion of participants with treatment-emergent non-serious adverse events and the number of treatment-emergent non-serious adverse events, overall, by system organ classification, by relatedness to study medication, and by severity
- 3. Incidence of adverse events leading to premature discontinuation of study medication, defined as the proportion of participants with treatment-emergent adverse events and the number of treatment-emergent adverse events that led to premature discontinuation of study medication, overall, by system organ classification, by relatedness to study medication, and by severity
- 4. Proportion of participants with abnormal laboratory tests for ALT, AST, total bilirubin, hemoglobin, hematocrit, and platelet count, proportion of participants with temperature ≥38.5°C (indicating fever), and proportion of participants with any edema (over all body locations and by each location) over the course of the 10-week intervention period
- 5. Percent change in eGFR from baseline to week 10
- 6. Percent change in UPCR from baseline to week 10
- 7. Proportion of participants achieving a nadir UPCR less than 1.5 g/g and at least a 40% reduction from baseline at week 10

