4.2.2 SECONDARY ENDPOINTS

- (1) Incidence of serious adverse events, adverse events and abnormal laboratory tests
- (2) Percent change of eGFR from baseline to week 10
- (3) Percent change in UPC from baseline to week 10
- (4) Proportion of participants achieving a nadir UPC less than 1.5 g/g and at least a 40% reduction from baseline at week 10.

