8.3 TIME PERIOD AND FREQUENCY FOR EVENT ASSESSMENT AND FOLLOW-UP

Participants should be monitored for adverse events throughout the study with the final assessment occurring at week 14.

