#### 6.2 Secondary Outcome Assessments

## 6.2.1 Safety measures

An adverse event is any untoward medical occurrence in a clinical study participant administered a medicinal (investigational or non-investigational) product. Adverse events, whether serious or non-serious, related or not related, are recorded after administration of adalimumab (i.e., are treatment-emergent events) until week 14. All serious adverse events that do resolve by the end of the study, or that do not resolve upon discontinuation of the subject's participation in the study, are followed until any of the following occurred:

- The event resolves
- The event stabilizes
- The event returns to baseline, if a baseline value/status were available
- The event can be attributed to agents other than the study drug or to factors unrelated to study conduct
- It becomes unlikely that any additional information can be obtained (participant or health care practitioner refusal to provide additional information, or lost to follow-up after demonstration of due diligence with follow-up efforts).

\*\* Optional procedures required if study visit is conducted in-person

Adverse events are categorized by severity and by relationship to study medication by the site investigators, and by system organ class by the coordinating center investigators.

The status of edema is important in this patient population as a manifestation of disease, so any edema (over all body locations and by each location) over the course of the 10-week intervention period is evaluated within the adverse event reporting as new or worse than prior to study.

As a clinically significant change, any fever event (temperature ≥38.5°C) is recorded over the course of the 10-week intervention period.

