#### 6.2.2 Laboratory abnormalities

For ALT, AST, and total bilirubin, the laboratory result value is abnormal when it is greater than 2 x upper limit of normal (ULN). Laboratory result values either below the age-matched lower limit of normal (LLN) or above the age-matched upper limit of normal is defined as laboratory abnormalities for hemoglobin, hematocrit, and platelet count. The age-matched normal ranges of ALT, AST, total bilirubin, hemoglobin, hematocrit, and platelet count are provided below:

	Age Group	Male	Female
ALT	> or =6 year	7-55 U/L	7-45 U/L
AST	6-13 years	8-60 U/L	8-50 U/L
	> or =14 years	8-48 U/L	8-43 U/L
Total bilirubin	6 to 17 years	0.0-1.0 mg/dL	0.0-1.0 mg/dL
Hemoglobin	6-8 years	11.5-14.3 g/dL	11.5-14.3 g/dL
	9-10 years	11.8-14.7 g/dL	11.8-14.7 g/dL
	11-14 years	12.4-15.7 g/dL	11.9-14.8 g/dL
	15-17 years	13.3-16.9 g/dL	11.9-14.8 g/dL
	Adults	13.2-16.6 g/dL	11.6-15.0 g/dL
Hematocrit	6-7 years	34-42%	34-42%
	8-11 years	35-43%	35-43%
	12-15 years	38-47%	35-43%
	16-17 years	40-50%	35-43%
	Adults	38.3-48.6%	35.5-44.9%
Platelet count	6-9 years	187-400 x 10  /L	187-400 x 10  /L
	10-13 years	177-381 x 10  /L	177-381 x 10  /L
	14-17 years	139-320 x 10  /L	158-362 x 10  /L
	Adults	135-317 x 10  /L	157-371 x 10  /L

We calculate the proportion of participants with laboratory abnormalities at weeks 2, 4, 8 and 10, and overall (i.e., a participant experienced a lab abnormality at any visit).

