- Table 17. Proportion of participants achieving a nadir UPCR <1.5 g/g and at least a 40% reduction from baseline at week 10. As-Treated Population.
- Table 18.1. Proportion of Participants with Abnormal Laboratory Tests for ALT, AST, Total Bilirubin, Hemoglobin, Hematocrit, and Platelet Count Over the Course of the 10-Week Intervention Period. As-Treated Population.
- Table 18.2. Shift Table for Normal and Abnormal Laboratory Test Changes from Screening to Weeks 0, 2, 8, 10, and 14 in ALT, AST, Total Bilirubin, Hemoglobin, Hematocrit, and Platelet Count. As-Treated Population.
- Table 19. Correlations between TNF activation score and urinary MCP1/uCr and TIMP1/uCr biomarker levels at baseline. As-Treated Population with Kidney Biopsy Tissue Collected within 12 Months of Study Baseline.

- Table 20.1. Change from baseline to weeks 2, 4, and 8 in urinary MCP1/uCr. As-Treated Population.
- Table 20.2. Percent change from baseline to weeks 2, 4, 8, and 10 in urinary MCP1/uCr. As-Treated Population.
- Table 20.3. Urinary MCP1/uCr values at baseline and weeks 2, 4, 8, and 10. As-Treated Population.
- Table 21.1. Change from baseline to weeks 2, 4, and 8 in urinary TIMP1/uCr. As-Treated Population.
- Table 21.2. Percent change from baseline to weeks 2, 4, 8, and 10 in urinary TIMP1/uCr. As-Treated Population.
- Table 21.3. Urinary TIMP1/uCr values at baseline and weeks 2, 4, 8, and 10. As-Treated Population.
- Table 22. Change in uEGF/uCr levels from baseline to weeks 2, 4, 8, and 10. As-Treated Population.
- Table 23. Correlation coefficient between uEGF/uCr at baseline with changes and percent changes in urinary MCP1/uCr and urinary TIMP1/uCr biomarker levels and in eGFR and UPCR values at week 10. As-Treated Population.
- Table 24. Changes in FSGS-MCD Patient Reported Outcome (PRO) score from baseline to weeks 2, 4, 8 and 10. As-Treated Population.

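### The SAP ends its edema, fever and laboratory-abnormality endpoints at week 10, although its adverse event window and one laboratory table run to week 14

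*SAP*

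**What the plan says.** SAP 4.2 item 4 groups abnormal laboratory tests, fever and edema, ending with the "proportion of participants with any edema (over all body locations and by each location) over the course of the 10-week intervention period". SAP 6.2.1 repeats the limit for fever ("any fever event (temperature ≥38.5°C) is recorded over the course of the 10-week intervention period") and for edema, which "over the course of the 10-week intervention period is evaluated within the adverse event reporting as new or worse than prior to study". SAP 9.2 applies a ten-week treatment period to all three, and the titles of Tables 14 (edema) and 18.1 (laboratory) carry ten weeks. Table 13 (fever) has no window in its title and takes its limit from 4.2 and 6.2.1.

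Other parts run longer. In SAP 6.2.1 adverse events "are recorded after administration of adalimumab (i.e., are treatment-emergent events) until week 14". Table 18.2 is titled "Shift Table for Normal and Abnormal Laboratory Test Changes from Screening to Weeks 0, 2, 8, 10, and 14". SAP 6.2.2 lists laboratory proportions at weeks 2, 4, 8 and 10 and then "overall (i.e., a participant experienced a lab abnormality at any visit".

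Protocol 8.3 says "Participants should be monitored for adverse events throughout the study with the final assessment occurring at week 14". Its safety endpoint in 4.2.2 is "Incidence of serious adverse events, adverse events and abnormal laboratory tests", with no time limit, whereas the eGFR and proteinuria endpoints beside it name week 10. The Protocol Summary gives an 8-week intervention and a 6-week follow-up after treatment.

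**The concern.** The ten-week period in the SAP matches no period in the protocol, and the SAP gives no reason for stopping there. With the last dose at week 8, the three endpoints cover only part of the post-treatment observation that the trial was set up to make.

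Two consequences follow. First, the same patient can be an event in one safety output and a non-event in another. Second, the protocol's laboratory endpoint has been narrowed without a record. SAP section 10 item 2 presents discontinuation events, fever and edema as additions, but does not say that abnormal laboratory tests, already in the protocol without a limit, now stop at week 10. Safety is a key secondary outcome and at most eight patients are treated, so one reclassified patient visibly changes a proportion.

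**Working it through.** The plan states no figure to reproduce, so the check sets the windows side by side and then does simple arithmetic.

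**Windows**

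| Item | Ends at | Source |
|---|---|---|
| Intervention (doses at weeks 0, 2, 4, 6, 8) | week 8 | Protocol Summary; protocol 6.1.7 |
| Follow-up after treatment | week 8 + 6 = 14 | Protocol Summary |
| Adverse event assessment, all participants | week 14 | Protocol 8.3, 8.4.1; SAP 6.2.1 |
| Week 14 laboratory tests, vital signs, examination | week 14, in-person visits only | Protocol 7.2.3, 7.2.5; SAP 5.4 |
| Edema endpoint (Table 14) | week 10 | SAP 4.2, 6.2.1, 9.2, 12.1 |
| Fever endpoint (Table 13) | week 10 | SAP 4.2, 6.2.1, 9.2 |
| Laboratory proportion (Table 18.1) | week 10 | SAP 4.2, 9.2, 12.1 |
| Laboratory shift table (Table 18.2) | week 14 | SAP 12.1 |

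**Share of follow-up left out**

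- From first dose: (14 − 10) / 14 = 4/14 = 29% of the weeks.
- After the last dose: (14 − 10) / (14 − 8) = 4/6 = 67% of the weeks, so 2 of 6 are kept.

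These are shares of time, not of events.

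**The rules applied to three patients**

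1. New non-serious edema at week 12, recorded as an adverse event: counted in Tables 11.1 to 11.3, not in Table 14.
2. Fever of 39°C at week 12, recorded as a non-serious adverse event: counted in Tables 11.1 to 11.3, not in Table 13.
3. ALT first above twice the upper limit of normal at an in-person week 14 visit: abnormal in Table 18.2 and plotted in Figure 6.1 (SAP 9.2 plots anyone abnormal during the study), but a non-event in Table 18.1.

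**Weight of one patient**

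100/n gives 100/8 = 12.5 points, 100/7 = 14.3 points and 100/6 = 16.7 points. The protocol sets eight as the maximum and six as the minimum evaluable sample.

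**Direction**

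For a cumulative proportion over the same participants, a longer window can add events but cannot remove any.

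**The case against.** The best defense is that week 10 is the last visit at which laboratory tests, vital signs and examination are scheduled for everyone. Week 14 may be a telephone call, so a laboratory proportion to week 14 mixes participants who were and were not tested. This stands for laboratory results and measured temperatures, and is a good reason to keep the week 10 figure. It does not cover edema, or fever reported as an adverse event, because adverse events are assessed at week 14 for everyone. Even there, the week 14 examination is optional.

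It is also fair to say that Tables 14 and 18.1 state their window, that fever and edema are documented SAP additions, and that the any-visit wording in 6.2.2 most naturally means the visits just listed. That wording is ambiguous rather than a clear contradiction.

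A reader might infer that late safety events are hidden. The documents do not support this: the adverse event tables and listings carry events to week 14, and Table 18.2 carries the laboratory shifts. A reader might also turn the 29% of follow-up time into a percentage by which the proportions are too low. That would require a constant event risk through the weeks off drug and a 14-week target. The documents give no event rate, and a ten-week proportion is not biased for a ten-week endpoint.

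**Conclusion.** The point holds as a minor inconsistency of windows. Three named safety endpoints stop at week 10, under a period label that the protocol does not use and without a stated reason. The SAP's treatment-emergent window, the reporting within which edema is evaluated, and Table 18.2 all reach week 14. Late edema and adverse-event-reported fever are left out of their own endpoints. A late laboratory abnormality is left out of Table 18.1 if the participant came in person.

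The effect is limited to descriptive tables. No test result changes and the events remain visible elsewhere. How many patients would move cannot be derived from the documents; each one moves a proportion by 12.5 points at n=8 or 16.7 at n=6. The conclusion rests on reading the ten-week phrase in 4.2 item 4 as covering all three endpoints, which 6.2.1, 9.2 and the title of Table 18.1 support.

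**What to change.** - **Edema and fever** (SAP 4.2 item 4, 6.2.1, 9.2, Tables 13 and 14): report from first dose through week 14, with the week 10 figure as a second row. For fever, count a participant when a visit temperature or an adverse event record documents at least 38.5°C.
- **Laboratory tests** (SAP 6.2.2, 9.2, Table 18.1): keep the week 10 proportion, and add a through-week-14 row showing the number with an in-person week 14 result. State which visits the overall figure in 6.2.2 covers.
- **Label**: replace the ten-week intervention or treatment period with wording that fits the protocol's 8-week intervention and 6-week follow-up, for example first dose through week 10.
- **Record**: state in SAP section 10 how the laboratory endpoint differs from protocol 4.2.2, and why.

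The cost is SAP wording and minor programming, with no new data. The downside is that week 14 laboratory and temperature data are missing for participants seen by telephone, so the number assessed must be shown beside each week 14 row.

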### 4.3 Exploratory Endpoints

- 1. In the subgroup of participants with kidney biopsy tissue collected within 12 months of study baseline, correlation coefficient between intra-renal gene expression of TNF (TNF activation score) [1] and urinary MCP1/uCr and TIMP1/uCr biomarker levels at baseline
- 2. Change from baseline to weeks 2, 4, and 8 in urinary MCP1/uCr
- Change from baseline to weeks 2, 4, and 8 in urinary TIMP1/uCr
- 4. Percent change from baseline to weeks 2, 4, 8, and 10 in urinary MCP1/uCr
- 5. Percent change from baseline to weeks 2, 4, 8, and 10 in urinary TIMP1/uCr
- 6. Urinary MCP1/uCr values at baseline and weeks 2, 4, 8, and 10
- 7. Urinary TIMP1/uCr values at baseline and weeks 2, 4, 8, and 10
- 8. Changes in urinary epidermal growth factor normalized to urinary creatinine (uEGF/uCr) biomarker levels from baseline to week 10
- 9. Correlation coefficient between uEGF/uCr at baseline with changes and percent changes in urinary MCP1/uCr and urinary TIMP1/uCr biomarker levels and in eGFR and UPCR values at week 10.
- Changes in FSGS-MCD Patient Reported Outcome (PRO) score from baseline to weeks 2,
   4, 8 and 10

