7.2.1 SCREENING VISIT

The screening visit will take place preferably within 2 weeks, but no more than 6 weeks prior to the baseline visit (Week 0)

At the screening visit:

- Patient/Parent provides written informed consent and HIPAA authorization prior to any evaluation or testing. Minor participants should provide assent in accordance with IRB guidelines
- b. A review of existing medical records and tests, provided by the patient or referring physician, will be performed to document the history of FSGS or TR-MCD and general medical history.
- c. Vital signs including height, weight, temperature and blood pressure are obtained.
- d. The patient undergoes a physical examination.
- e. The patient has blood and spot urine collected for monitoring labs, including urine pregnancy test (if applicable).
- f. A spot urine sample is obtained for measurement of target engagement biomarkers
- g. If the patient consents, biorepository samples should be obtained
- h. Archived kidney biopsy tissue is requested to be sent [when available and if not already submitted to the NEPTUNE study] to the laboratory at the University of Michigan for gene expression profiling for mechanisms of disease
- i. Archived kidney biopsy report is anonymized and uploaded into the study electronic data capture system for central review

At Screening, a preliminary evaluation is performed and once screening is complete, if all inclusion and no exclusion criteria are met, the patient is deemed eligible and will be asked to return for the baseline visit for study drug initiation. Subjects who have not met study enrollment criteria will be considered a screen failure and their study participation will end.

Repeat Screening. If the patient is found to be ineligible, a repeat screening visit may be performed at the local clinician investigator's discretion.

Once eligibility is confirmed, the patient should be instructed to bring a 24-hour urine specimen to the baseline visit.

7.2.2 BASELINE/WEEK 0

The Baseline visit/Week 0 will occur within 6 weeks of the screening evaluation. The following procedures will take place at the baseline visit:

- a) Interval medical history
- b) Review of concomitant medications
- c) Physical examination
- d) Assessment of adverse events
- e) Vital signs will be obtained including weight, blood pressure, and temperature
- f) Subject to complete HRQOL assessment

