## 6. Outcomes

## 6.1 Primary Outcome Assessments

Spot urinary biospecimens to assay MCP1 (ng/mL), TIMP1 (ng/mL) and creatinine (mg/mL) are collected with spot urine tests at screening and weeks 0, 2, 8, and 10. Urine creatinine is used to normalize the urinary MCP1 and urinary TIMP1 by calculating the ratio of urinary MCP1 and urinary creatinine and the ratio of urinary TIMP1 and urinary creatinine.

Urinary MCP1 and Urinary TIMP1 are measured by ELISA methods [2]. There are no published reference ranges for the urinary MCP1/uCr nor urinary TIMP1/uCr levels; however, lower values for both biomarkers are associated with less intra-renal TNF activation. [1] Thus, either absolute or relative changes from baseline to post-treatment time points indicate TNF pathway target engagement by adalimumab and support the proof of concept of this trial.

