## 6.4 Exploratory Outcome Measures

Intra-renal gene expression of TNF is derived from archived biopsy tissue of study participants or from the Nephrotic Syndrome Study Network (NEPTUNE) study data using the NEPTUNE study protocol and as published. [3] This parameter was only included for participants with biopsies within one year of consent in the TNF pilot study and is generated as a TNF activation score.

A TNF activation network was generated from expert curated interactions from NETPro annotations in the Genomatix Genome Analyzer database (Precigen Bioinformatics).[1] It was based on renal biopsy specimens available from more than 250 NEPTUNE participants with MCD and FSGS. From the database, causally downstream genes or proteins that increased expression from TNF exposure were used to generate a TNF activation score. Individual gene expression values were first Z-transformed. The TNF activation score for each participant was the average Z-score of the genes in their kidney RNA-seq profile and defines the intra-renal gene expression of TNF measure.

Urinary epidermal growth factor (uEGF, ng/ml) biomarker levels are assessed from spot urine specimens collected and normalized by urinary creatinine (mg/ml) at Screening, and Weeks 0, 2, 8, and 10. Higher levels of uEGF/uCr (ng/mg) indicate better kidney function.

The FSGS-MCD Patient Reported Outcome (PRO) score is still in development and scoring methods have not yet been finalized. The score will be derived from the FSGS-MCD PRO structured questionnaires completed by participants at in-person study visits at Weeks 0, 2, 8 and 10. The analyses of FSGS-MCD PRO scores will occur when the scoring methods have been developed and made available to the study investigators.

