## 9.4 Exploratory Analyses

Spearman correlations and scatterplots are provided to assess the correlation of TNF activation score and urinary MCP1/uCr and urinary TIMP1/uCr biomarker levels at baseline, and the correlation of uEGF/uCr at baseline with changes and percent changes in urinary MCP1/uCr and urinary TIMP1/uCr biomarker levels and in eGFR and UPCR values at week 10.

Continuous outcomes (e.g., eGFR, uEGF/uCr biomarker levels) will be summarized descriptively, including baseline, follow-up and changes from baseline and graphically as spaghetti plots of participants' changes (absolute and relative) over time and values over time.

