## 12.3 List of Figures

- Figure 1. CONSORT diagram. All Subjects.
- Figure 2.1. Spaghetti plot of changes from baseline to weeks 2, 4, 8, and 10 in urinary MCP1/uCr. As-Treated Population.
- Figure 2.2. Spaghetti plot of percent changes from baseline to weeks 2, 4, 8, and 10 in urinary MCP1/uCr. As-Treated Population.
- Figure 2.3. Spaghetti plot of urinary MCP1/uCr at baseline and weeks 0, 2, 4, 8, and 10. As-Treated Population.
- Figure 3.1. Spaghetti plot of changes from baseline to weeks 2, 4, 8, and 10 in urinary TIMP1/uCr. As-Treated Population.

- Figure 3.2. Spaghetti plot of percent changes from baseline to weeks 2, 4, 8, and 10 in urinary TIMP1/uCr. As-Treated Population.
- Figure 3.3. Spaghetti plot of urinary TIMP1/uCr at baseline and weeks 2, 4, 8, and 10. As-Treated Population.
- Figure 4.1. Spaghetti plot of changes from baseline to weeks 2, 4, 8, and 10 in eGFR. As-Treated Population.
- Figure 4.2. Spaghetti plot of percent changes from baseline to weeks 2, 4, 8, and 10 in eGFR. As-Treated Population.
- Figure 4.3. Spaghetti plot of eGFR at baseline and weeks 2, 4, 8, and 10. As-Treated Population.
- Figure 5.1. Spaghetti plot of changes from baseline to weeks 2, 4, 8, and 10 in UPCR. As-Treated Population.
- Figure 5.2. Spaghetti plot of percent changes from baseline to weeks 2, 4, 8, and 10 in UPCR. As-Treated Population.
- Figure 5.3. Spaghetti plot of UPCR at baseline and weeks 2, 4, 8, and 10. As-Treated Population.
- Figure 6.1. Spaghetti plot of participants with at least one abnormal laboratory value: ALT. As-Treated Population.
- Figure 6.2. Spaghetti plot of participants with at least one abnormal laboratory value: AST. As-Treated Population.
- Figure 6.3. Spaghetti plot of participants with at least one abnormal laboratory value: Total Bilirubin. As-Treated Population.
- Figure 6.4. Spaghetti plot of participants with at least one abnormal laboratory value: Hemoglobin. As-Treated Population.
- Figure 6.5. Spaghetti plot of participants with at least one abnormal laboratory value: Hematocrit. As-Treated Population.
- Figure 6.6. Spaghetti plot of participants with at least one abnormal laboratory value: Platelet Count. As-Treated Population.
- Figure 7.1. Scatterplot of TNF activation score and baseline urinary MCP1/uCr. As-Treated Population.
- Figure 7.2. Scatterplot of TNF activation score and baseline urinary TIMP1/uCr. As-Treated Population.

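### The exploratory correlations of baseline uEGF/uCr with week-10 changes in MCP1/uCr and TIMP1/uCr share the week-0 urine creatinine, which can tilt them negative; a screening-sample version should be reported beside them

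*SAP*

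**What the plan says.** SAP 4.3 item 9 lists a "Correlation coefficient between uEGF/uCr at baseline with changes and percent changes in urinary MCP1/uCr and urinary TIMP1/uCr biomarker levels", and extends it to eGFR and UPCR. SAP 9.4 makes these Spearman correlations with scatterplots. For the two biomarkers the outputs are Table 23 and Figures 9.1, 9.2, 10.1 and 10.2. Item 9 is not among the exploratory endpoints in Protocol 4.2.3; the SAP added it.

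On the denominators, SAP 6.1 states that "Urine creatinine is used to normalize the urinary MCP1 and urinary TIMP1". SAP 6.4 says that uEGF "biomarker levels are assessed from spot urine specimens collected and normalized by urinary creatinine (mg/ml) at Screening, and Weeks 0, 2, 8, and 10". Its note on assay quality names urine creatinine once, beside MCP1, TIMP1 and EGF, and puts all time points on one plate. Protocol 7.2.2 lists one spot collection for biomarkers at the baseline visit.

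The SAP does not define baseline. Protocol 7.2.2 treats it as Week 0, and Protocol 7.2.1 places screening "no more than 6 weeks prior to the baseline visit (Week 0"). One SAP figure title blurs this: "Spaghetti plot of urinary MCP1/uCr at baseline and weeks 0, 2, 4, 8, and 10". I read baseline as Week 0. Neither document mentions the shared denominator or adjusts for it.

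**The concern.** The week-0 creatinine divides the predictor (uEGF/uCr) and also the starting value from which the change is measured. Suppose that creatinine is low at week 0 for a reason unrelated to dilution, such as assay error or a short-term shift in excretion. uEGF/uCr is then too high. Baseline MCP1/uCr and TIMP1/uCr are also too high, so the change to week 10 looks more negative. The push has the same sign for absolute and percent change.

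SAP 6.4 takes higher uEGF/uCr to mean better kidney function. The artefact would therefore resemble a finding that patients with better kidney function show more target engagement. With 6 to 8 patients that could be taken as a lead on who responds.

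**Working it through.** The documents give no expected correlation or SD for this analysis, so there is no planned figure to reproduce. Every SD below is an assumption.

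**Inputs.** From the documents: 6 to 8 patients (Protocol 4.1; SAP 9.5 uses 7) and Spearman correlation (SAP 9.4). Assumed, on the log scale:
- s_C, visit-to-visit SD of creatinine not due to dilution: 0.1 to 0.4. Dilution cancels within each ratio and is left out.
- s_E, SD of uEGF across patients: 0.4 to 0.6.
- s_M, within-patient visit-to-visit SD of the marker: 0.25 to 0.5.

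**Step 1, log-scale correlation with no true relation.** The predictor is e - c0. The log ratio of week 10 to week 0 is (m10 - m0) - c10 + c0. Their covariance is -s_C², so

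r = -s_C² / √[(s_E² + s_C²)(2s_M² + 2s_C²)].

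Percent change rises strictly with the log ratio, so the two give identical Spearman coefficients.

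**Step 2, expected Spearman at n patients** (bivariate normal):

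E = 6/[π(n+1)] × [asin r + (n-2) asin(r/2)].

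**Worked case:** s_C = 0.3, s_E = 0.4, s_M = 0.25, n = 8. r = -0.09/√(0.25 × 0.305) = -0.09/0.276 = -0.326. E = -0.2122 × [0.332 + 6 × 0.1637] = -0.279.

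| s_C | s_E 0.4, s_M 0.25: r, then expected Spearman | s_E 0.6, s_M 0.5: r, then expected Spearman |
|---|---|---|
| 0.1 | -0.064, -0.054 | -0.023, -0.019 |
| 0.2 | -0.198, -0.168 | -0.083, -0.071 |
| 0.3 | -0.326, -0.279 | -0.163, -0.138 |
| 0.4 | -0.424, -0.365 | -0.245, -0.209 |

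Simulation at n = 8 agrees. For absolute change (between-patient marker log-SD 0.8, no mean change) it gives about -0.02 to -0.05 at s_C = 0.1 and -0.06 to -0.33 at 0.2 to 0.4. Across both measures the range is about -0.02 to -0.06 at 0.1 and -0.06 to -0.37 at 0.2 to 0.4.

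**Step 3, against chance.** The null standard error is 1/√(n-1): 0.45, 0.41 and 0.38 for n = 6, 7 and 8. The shift is smaller than this but goes one way. At n = 7 with s_E = 0.4, s_M = 0.25 and s_C = 0.3, a correlation of -0.5 or stronger appears in 32% to 34% of null trials, against 13% with the screening sample.

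**Step 4, screening uEGF/uCr as predictor.** It carries the screening creatinine, which is absent from both ends of the change. The covariance with the log ratio is then zero, and simulation puts the mean Spearman within 0.01 of zero for percent change.

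**Step 5, what remains for absolute change.** A patient's lasting creatinine level scales the screening, week-0 and week-10 ratios alike. It cancels in percent change but not in absolute change once the marker falls. Assumptions: n = 7, s_C = 0.2, lasting creatinine log-SD 0.3 to 0.5, mean log change -0.5 to -1.0, uEGF log-SD 0.5 between and 0.2 within patients, marker log-SD 0.4 to 0.7 between and 0.4 within, response log-SD 0.3. The mean Spearman is -0.05 to -0.23 with screening uEGF/uCr and -0.13 to -0.30 with week-0. If 25% of screened patients are selected on the screening ratio, these become -0.01 to -0.12 and -0.11 to -0.22.

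**Step 6, the price.** In large-sample simulation at s_C = 0.2, a real Spearman of -0.38 is seen as -0.31 to -0.34 with the screening sample and -0.39 to -0.44 with week-0. At s_C = 0.4, a real -0.32 is seen as -0.23 to -0.25 and -0.47 to -0.51.

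**The case against.** The strongest reply has four parts.

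- **Size.** It rests on an assumed SD. Dilution cancels, a single plate limits batch error, and at a log-SD of 0.1 the effect is trivial. This stands. A reader might infer that the plan guarantees a false negative correlation; the documents do not support that, because they give no information on creatinine variation other than dilution.
- **Remedy.** A reader might infer that the screening sample removes the problem entirely and free of cost. Step 5 shows that it does not for absolute change. The screening urine also decides eligibility (Protocol 2.2), may be up to 6 weeks old, and may be repeated (Protocol 7.2.1). This stands, and it is why the screening version belongs beside the planned one and not in its place.
- **Scope.** A reader might extend the point to every item 9 figure. Figures 11.1 and 11.2 use eGFR, which SAP 8.2.1 computes from serum creatinine, so no urine creatinine is shared. For UPCR, Protocol 7.2.2 lists a 24-hour or first-morning urine separately from the biomarker spot urine, so Figures 12.1 and 12.3 are probably clear too. This stands.
- **Consequence.** The SAP calls its analyses primarily descriptive (7.1), and neither document says that uEGF will select patients for a later trial. This stands and limits the importance. It does not excuse a one-directional distortion: a coefficient judged by its size is misread when its size is shifted.

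**Conclusion.** The point holds in a limited form. The SAP does not say outright that one creatinine value serves all three markers, but its assay description and the single week-0 biomarker collection make that the natural reading. Nothing in the SAP corrects for it.

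The bias is negative for both absolute and percent change. Its size is conditional: negligible if creatinine variation other than dilution is near a log-SD of 0.1, and material at 0.3 to 0.4, where it approaches one null standard error. Screening uEGF/uCr removes it for percent change, provided that creatinine errors at screening are independent of those at weeks 0 and 10. For absolute change it only reduces it.

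This is an inexpensive improvement to an exploratory analysis. Primary and secondary endpoints are unaffected.

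**What to change.** In SAP 4.3 item 9, SAP 9.4 and Table 23, for MCP1/uCr and TIMP1/uCr only:

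1. Name Week 0 as the baseline, and keep the planned week-0 correlations.
2. Add the Spearman correlation of screening uEGF/uCr with percent (equivalently, log-ratio) change from week 0 to week 10. If screening was repeated, use the sample that qualified the patient.
3. Base any statement about uEGF as a predictor on that added version.
4. Footnote the shared creatinine on the week-0 rows of Table 23 and on Figures 9.1 to 10.2. State that the absolute-change versions are descriptive, because lasting differences in creatinine between patients can leave a residual correlation whichever sample is used.

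Leave Figures 11.1 and 11.2 as they are. Leave Figures 12.1 and 12.3 too, unless UPCR was taken from the same week-0 spot urine.

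The cost is a few lines of SAP text and a few extra coefficients. Screening uEGF/uCr is already measured, so no samples or assays are added. The scientific cost is a predictor up to 6 weeks older, taken from the selection sample, that somewhat understates a real correlation.
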